#### Storing

All ECGs will be stored electronically on the Muse Cardiology Information System (█████████████████████).

#### Data transfer

For time points specified in the Flow Chart, ECGs will be transferred electronically to the central ECG lab for evaluation and/or storage, except for ECGs from screening and EoT visits, which will not be transferred.

In case of repeat ECGs due to quality reasons, only the repeated ECG recordings will be transferred to the central ECG lab, whereas the initially recorded ECGs will be discarded. Unscheduled ECGs (for safety reasons) will be transferred to the central ECG lab but will not be included into the statistical analysis of interval lengths.

Data transfer from the central ECG lab to the sponsor is described in the ECG data transfer agreement (see TMF).

#### Evaluation

##### a) Central ECG lab

Central ECG lab evaluation will be performed post-study for the first of three replicate ECGs per time point on Days 1 to 3 and, for the single ECGs, on Days 4 and 5. This will include the determination of cardiac QRS-axis as assessed by the ECG machine's algorithm, as well as the intervals RR, PR, QRS and QT measured semi-automatically.

Heart rate (HR) and the QT interval corrected for HR (QTc, e.g. QTcF and QTcB) will be determined by the sponsor (see trial statistical analysis plan (TSAP) for details).

All semi-automatic interval measurements in one subject will be performed on the same lead. The intervals will be measured from four cardiac cycles (beats) in lead II. If lead II shows a flat T wave or is not measurable for any reason, lead V5 will be

Proprietary confidential information © 2021 Boehringer Ingelheim International GmbH or one or more of its affiliated companies

used, or if that lead is not measurable, then lead I will be used. The lead actually used will be reported in the CTR. For automatic interval measurements, no lead will be provided. After quality control, the fiducial point markings will be reviewed by the cardiologist assigned to the study.

Evaluation of ECGs will comply with the ICH E14 guidance document and supplements [[R07-4722](#), [R16-0366](#)] as well as the FDA requirements for annotated digital ECGs [[R09-4830](#)].

b) Trial site

All local ECGs will be evaluated by the investigator or a designee.

For the inclusion or exclusion (see Section [3.3](#)) of a subject and for the assessment of cardiac safety during the study, the QT and QTcB values generated by the computerised ECG system or their manual corrections by the investigators will be used. In doubtful cases, ECGs may be sent upfront (i.e. prior to the regular data transfer) for cardiologic assessment by the central lab. In this case, these centrally measured results would overrule any other results obtained.

Abnormal findings, irrespective of whether they originate from central or local evaluation, will be reported as AEs (during the trial) or baseline conditions (at screening), if judged clinically relevant by the investigator. Any ECG abnormalities will be monitored carefully and, if necessary, the subject will be removed from the trial and will receive the appropriate medical treatment.

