## Safety measures

The following safety measures will be applied in order to minimize the risk for healthy volunteers:

- Careful dose selection, no dose will be included which has not been previously studied in the FIH study.
- The dose escalation factor is limited to 2.
- Repeated safety laboratory tests will be performed before and during the treatment period (refer to [Flow Chart](#) and see Section [5.2.4](#)). This will also include sensitive serum markers to detect early skeletal muscle injury.
- An ECG monitoring up to Day 5 (96 h post dose) will be performed to cover the anticipated period of highest drug exposure. Continuous ECG measurement will be performed over 4 hours post dose. Dose escalation will be stopped immediately, if at least 2 subjects at one dose level show relevant QT prolongation (see Section [3.3.4.2](#) for details).
- Orthostatic testing will be performed prior to and following study drug administration at the time points indicated in the Flow Chart to assess hemodynamic effects of BI 474121. Dose escalation will be stopped, if clinical symptoms are observed in more than 1 subject (severe) or in more than 3 subjects (moderate) in one dose group.

Proprietary confidential information © 2021 Boehringer Ingelheim International GmbH or one or more of its affiliated companies

- Only if the respective dose of BI 474121 is safe, shows acceptable tolerability, and if no stopping criterion was met (see Section [3.3.4.2](#)), the next higher dose will be given not earlier than 7 days after first dosing of the previous dose group (referring to the 1st subject of each respective dose group). A documented Safety Review must take place prior to each dose escalation (see Section [3.1](#)).
- The subjects will stay at the trial site for at least 48 hours after study drug administration. Based on observed half-life of BI 474121 of ~20 hours in FIH study, this is expected to cover the period of highest risk / peak effect.
- During in-house confinement, the subjects will be under medical observation and thoroughly monitored for both expected and unexpected adverse events.
- SARS-CoV-2 specific test will be conducted at screening visit and within 3 days prior to admission to trial site. Subjects positive in the SARS-CoV-2 test are not eligible to the trial in accordance to exclusion criterion 25 and will be excluded from the trial.

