Although no formal Safety Review meeting will take place within a given dose group, safety will be continuously monitored during this trial, and an individual will only be dosed in the absence of any safety concern (i.e. no dose-limiting events occurred) and if none of the pre-specified trial-specific stopping criteria have been met (refer to Section [3.3.4.2](#)).

The minimum data set for review consists of the following:

- AEs in the current and preceding dose groups up to at least 48 h post dosing, including clinically relevant findings from ancillary safety testing listed below (Note:

AEs may be ongoing at the time of Safety Reviews and AE information may be subject to change prior to Database Lock)

- Results from 12-lead ECG and continuous ECG monitoring in the current and preceding dose groups up to at least 48 h post dosing
- Vital signs and results from the orthostatic tests in the current and preceding dose groups up to at least 48 h post dosing
- Clinical laboratory tests in the current and preceding dose groups up to at least 48 h post dosing
- Check of criteria for stopping subject treatment as per Section [3.3.4.1](#)

The decision to escalate the dose will be made jointly by the Principal Investigator (or an authorised deputy) and the Clinical Trial Leader (CTL) (or an authorised deputy) after in-depth analysis of all available safety data, especially SAEs (if occurred), AEs, and out-of-range laboratory results (if considered clinically significant). In addition and depending on the results and findings, suitable experts from the sponsor or external institutions may be consulted on an as needed basis. In these cases expert recommendations will be documented in the minutes of the Safety Review and considered for the decision making. Dose escalation will only be permitted if no safety concerns exist neither in the opinion of the Principal Investigator (or an authorised deputy) nor in the opinion of the CTL (or an authorised deputy).

Safety Reviews can be conducted face-to-face or by video/telephone conference. The CTL is responsible for the organisation and minutes of the reviews. Minutes will be signed off by the Principal Investigator (or an authorised deputy) and CTL (or an authorised deputy), and will be filed in the investigator site file (ISF) and trial master file (TMF).

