#### **3.3.3 Exclusion criteria**

Subjects will not be allowed to participate, if any of the following general criteria apply:

Proprietary confidential information © 2021 Boehringer Ingelheim International GmbH or one or more of its affiliated companies

1. Any finding in the medical examination (including BP, PR or ECG) deviating from normal and assessed as clinically relevant by the investigator at screening visit
2. Repeated measurement of systolic blood pressure outside the range of 100 to 140 mmHg, diastolic blood pressure outside the range of 50 to 90 mmHg, or pulse rate outside the range of 50 to 90 bpm at screening visit
3. Any laboratory value outside the reference range that the investigator considers to be of clinical relevance at screening visit
4. Any evidence of a concomitant disease assessed as clinically relevant by the investigator
  - Gastrointestinal, hepatic, renal, respiratory, cardiovascular, metabolic, immunological or hormonal disorders
  - Diseases of the central nervous system (including but not limited to any kind of seizures or stroke), and other relevant neurological or psychiatric disorders
  - Chronic or relevant acute infections including viral hepatitis, human immunodeficiency virus (HIV) and/or syphilis.
5. History of cholecystectomy or other surgery of the gastrointestinal tract that could interfere with the pharmacokinetics of the trial medication (except appendectomy or simple hernia repair)
6. History of relevant orthostatic hypotension, fainting spells, or blackouts
7. History of relevant allergy or hypersensitivity (including allergy to the trial medication or its excipients)
8. Use of drugs within 30 days of planned administration of trial medication that might reasonably influence the results of the trial (including drugs that cause QT/QTc interval prolongation)
9. Intake of an investigational drug in another clinical trial within 60 days of planned administration of investigational drug in the current trial, or concurrent participation in another clinical trial in which investigational drug is administered
10. Smoker (more than 10 cigarettes or 3 cigars or 3 pipes per day)
11. Inability to refrain from smoking on specified trial days
12. Alcohol abuse (consumption of more 24 g per day)
13. Drug abuse or positive drug screening

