14. Blood donation of more than 400 mL within 12 weeks or 200 mL within 30 days or plasma donation within 2 weeks prior to trial drug administration, or intended blood donation during the trial
15. Intention to perform excessive physical activities within one week prior to the administration of trial medication or during the trial
16. Inability to comply with the dietary regimen of the trial site
17. A marked baseline prolongation of QT/QTc interval (such as QTc intervals that are repeatedly greater than 450 ms) or any other relevant ECG finding at screening visit
18. A history of additional risk factors for *Torsade de Pointes* (such as heart failure, hypokalaemia, or family history of Long QT Syndrome)

Proprietary confidential information © 2021 Boehringer Ingelheim International GmbH or one or more of its affiliated companies

19. Subject is assessed as unsuitable for inclusion by the investigator, for instance, because the subject is not considered able to understand and comply with study requirements, or has a condition that would not allow safe participation in the study
20. ALT (alanine transaminase), AST, or serum creatinine exceed upper limit of normal range at screening visit, confirmed by a repeat test
21. Orthostatic hypotension during orthostatic testing at between Day -3 to -1, that the investigator considers to be of clinical relevance.
22. A positive for SARS-CoV-2 specific test and clinical symptoms suggestive for this disease at screening visit or within 3 days prior to admission to trial site.

For study restrictions, refer to Section [4.2.2](#).

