#### **3.3.4.2 Discontinuation of the trial by the sponsor**

Boehringer Ingelheim reserves the right to discontinue the trial at any time for any of the following reasons:

1. Failure to meet expected enrolment goals
2. New toxicological findings, serious adverse events, or any safety information invalidating the earlier positive benefit-risk assessment.
3. Violation of GCP, or the clinical trial protocol (CTP), or the contract with BI impairing the appropriate conduct of the trial.
4. The sponsor decides to discontinue the further development of the investigational product
5. Dose escalation will be stopped if at least 2 subjects on active treatment at one dose level have relevant individual QT prolongations, i.e. a QTc increase of greater than 60 ms from baseline, or absolute QT or QTc greater than 500 ms, as confirmed by a repeat ECG recording
6. Occurrence of severe non-serious adverse events considered as drug-related by the investigator in 2 subjects of the same dose group (8 subjects), or occurrence of at least one drug-related serious adverse event. Moreover, dose escalation will be terminated if more than 3 of the actively dosed subjects at one dose level show drug-related and clinically relevant adverse events of at least moderate intensity.

The investigator / trial site will be reimbursed for reasonable expenses incurred in case of trial termination (except if item 3 applies).

Proprietary confidential information © 2021 Boehringer Ingelheim International GmbH or one or more of its affiliated companies

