## **5.2.5      Electrocardiogram**

### **5.2.5.1      12-lead resting ECG**

#### **Recording**

Twelve-lead resting ECGs (I, II, III, aVR, aVL, aVF, V1 - V6) will be recorded using a computerised electrocardiograph at the time points given in the [Flow Chart](#). Electrode placement will be performed according to the method of Wilson, Goldberger and Einthoven modified by Mason and Likar (hips and shoulders instead of ankles and wrists). Precise electrode placement will be marked with an indelible mark on the skin to allow reproducible placement throughout the study.

To achieve a stable heart rate at rest and to assure high quality recordings, the site personnel will be instructed to assure a relaxed and quiet environment, so that all subjects are at complete rest.

Proprietary confidential information © 2021 Boehringer Ingelheim International GmbH or one or more of its affiliated companies

All ECGs will be recorded for a 10 sec duration after subjects have rested for at least 5 min in a supine position. ECG recording will always precede all other study procedures scheduled for the same time (except for blood drawing from an intravenous cannula that is already in place) to avoid compromising ECG quality.

ECGs will be recorded as single ECGs or as triplicate ECGs (i.e. three single ECGs recorded within 180 sec) as indicated in the [Flow Chart](#).

ECGs may be repeated for quality reasons for instance due to alternating current artefacts, muscle movements, or electrode dislocation. For repetition within triplicate ECGs the time window of 180 sec applies as well. The repeat ECGs are assigned to the respective scheduled time point.

Additional (unscheduled) ECGs may be recorded for safety reasons. These ECGs are assigned to the prior scheduled time point in the sponsor's database.

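### The +60 ms QTc limb of the escalation stop is read on Bazett at the site, so when heart rate falls a QTcF rise above 60 ms can pass; add QTcF to the trigger alongside QTcB.

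*Protocol*

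**What the plan says.** Protocol 3.3.4.2 item 5 stops dose escalation if at least two actively treated subjects at one dose level show "a QTc increase of greater than 60 ms from baseline, or absolute QT or QTc greater than 500 ms", confirmed by a repeat ECG. The item does not name a correction, and the abbreviation list allows either Fridericia or Bazett.

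Protocol 5.2.5.1 (Evaluation, b) Trial site) supplies it. For entry decisions and for cardiac safety during the study, the site uses "the QT and QTcB values generated by the computerised ECG system" or the investigator's manual corrections. Doubtful ECGs may be sent to the central laboratory ahead of schedule, and its result then prevails. The correction to be applied to that result is not stated.

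Otherwise "Central ECG lab evaluation will be performed post-study". The review before each escalation needs "Results from 12-lead ECG and continuous ECG monitoring in the current and preceding dose groups up to at least 48 h post dosing" (Protocol 3.1), so in routine operation it works from the site's values.

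SAP 7.8.4 tabulates QTcF, models the change in QTcF against plasma concentration, and checks the slope of QTcF against RR. QTcB is only listed.

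**The concern.** The stop and the analysis use different heart-rate corrections. They agree at 60 bpm and diverge elsewhere, so the two changes from baseline differ whenever heart rate differs between baseline and the later ECG.

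The +60 ms limb is the exposed one. It compares two recordings that may be at different heart rates, and item 5 has no limit on the change in uncorrected QT. If heart rate falls after dosing, the Bazett change understates the Fridericia change. Two subjects could then have QTcF rises above 60 ms without meeting the stop, although the SAP would later show those rises. If heart rate rises, the reverse happens and escalation may stop early. That costs Japanese data at the higher doses but errs towards safety.

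**Working it through.** **Inputs from the documents.** Change limit 60 ms and absolute limit 500 ms (Protocol 3.3.4.2 item 5); QT and QTcB at the site (5.2.5.1 b); entry pulse 50 to 90 bpm (3.3.3, criterion 2: "pulse rate outside the range of 50 to 90 bpm at screening visit").

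**Assumptions, not in the documents.** Baseline QTcF 400 ms (range 380 to 450 ms) and heart-rate shifts of 5 to 10 bpm. ECGs follow at least 5 min of supine rest (5.2.5.1, Recording), so modest shifts are the relevant case. The 60 ms limit is a fixed rule, so there is no derived figure of the plan to reproduce.

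**Formulas.** With RR = 60/HR in seconds, QTcB = QT/RR^(1/2) and QTcF = QT/RR^(1/3). Write f(HR) = (HR/60)^(1/6). Then:

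- QTcB = QTcF x f(HR)
- QT = QTcF x (60/HR)^(1/3)
- QTcF rise at which the QTcB rise is 60 ms = [Q0 x f(HR0) + 60]/f(HR1) - Q0

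**The +60 ms limb, Q0 = 400 ms.** For 70 to 60 bpm, f(70) = 1.0260 and f(60) = 1, so the result is 400 x 1.0260 + 60 - 400 = 70.4 ms. For 65 to 60 bpm, f(65) = 1.0134, giving 65.4 ms. For 60 to 70 bpm, 460/1.0260 - 400 = 48.3 ms.

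| Heart rate (bpm) | QTcF rise at the QTcB trigger (ms) |
|---|---|
| 65 to 60 | 65.4 |
| 70 to 60 | 70.4 |
| 80 to 70 | 67.5 |
| 90 to 80 | 65.1 |
| 60 to 65 | 53.9 |
| 60 to 70 | 48.3 |

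For a 10 bpm fall from any starting rate in 50 to 90 bpm, with baseline QTcF 380 to 450 ms, the figure runs from about 65 ms (64.7: 90 to 80 bpm, 380 ms) to about 81 ms (81.2: 50 to 40 bpm, 450 ms). This is before the 500 ms limbs are considered.

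**Effect of the 500 ms limbs.** In QTcF terms they fire at the smaller of 500/f(HR) (by QTcB) and 500 x (HR/60)^(1/3) (by QT). That is 470.5 ms at 50 bpm (by QT), 500 ms at 60 bpm, and by QTcB 487.3 ms at 70 and 476.6 ms at 80 bpm. The value never exceeds 500 ms, with three consequences:

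- With a baseline QTcF of 440 ms or more, a 500 ms limb is reached by the time QTcF has risen 500 - 440 = 60 ms, so no gap remains.
- For 60 to 50 bpm at baseline 400 ms, the QTcB change would need a QTcF rise of 74.2 ms, but uncorrected QT fires first at 470.5 - 400 = 70.5 ms. A gap remains, slightly smaller.
- For 50 to 40 bpm at baseline 400 ms, QT fires at 500 x (40/60)^(1/3) - 400 = 36.8 ms. There is no gap, so the upper end of the 65 to 81 ms range is not reached in practice.

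**A case that passes every limb.** QTcF goes from 400 to 468 ms while heart rate goes from 70 to 60 bpm. Baseline QTcB is 410.4 ms. At 60 bpm QT, QTcB and QTcF are all 468 ms. The QTcB rise is 57.6 ms, nothing exceeds 500 ms, and the QTcF rise is 68 ms.

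**The case against.** The strongest reply is that this is a stated choice. The site has a defined correction, and a real-time safety screen need not share one with an exploratory concentration model. That much stands: nothing in the documents is contradicted. But it does not explain why a QTcF rise above 60 ms should escape the stop when heart rate falls.

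A second reply is that Bazett is the protective metric in the likelier direction. Protocol 5.4 reports vasodilation in animals, which would suggest a rise in heart rate. This stands against the tempting remedy of replacing QTcB by QTcF. At baseline 400 ms that would move the trigger from a QTcF rise of 48.3 to 60 ms for 60 to 70 bpm, which loosens a stop in healthy volunteers. It is no argument against adding QTcF.

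Third, other safeguards exist. Two active subjects must qualify, each confirmed by repeat ECG. Neither the Principal Investigator nor the Clinical Trial Leader may have a safety concern. Doubtful ECGs can go to the central laboratory, and uncorrected QT is also seen: in the case above it rises from 380.0 to 468 ms, which a careful reader might notice. These points limit the harm, but the central referral and the clinical judgement are discretionary, and a QTcB rise just under 60 ms need not look doubtful.

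Fourth, the drug profile in Protocol 1.2 is largely blacked out, and the SAP's additional Section 10 cannot be seen. First-in-human heart-rate data may exist, and the correction used for the SAP's categorical QTc endpoints cannot be confirmed. This stands as a limit on the point.

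Finally, the site's machine readings and the central semi-automatic readings will differ anyway. That is true, but it is a separate source of difference and does not justify the gap.

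**Conclusion.** The point holds, and its consequence is minor. In routine operation the +60 ms limb runs on QTcB. At an assumed baseline QTcF of 400 ms, a fall of 5 to 10 bpm to 60 bpm lets QTcF rise by up to 65.4 to 70.4 ms before item 5 fires. The gap exists only for baseline QTcF below 440 ms, and the 500 ms limbs narrow or close it at some heart rates.

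A reader might go further in four ways that the documents do not support:

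- That the site's correction is undefined. Protocol 5.2.5.1 b) defines it.
- That BI 474121 lowers heart rate, so that late stops are to be expected. No shift is given in the visible text, and the SAP models heart rate against concentration as an open question.
- That early stopping on QTcB is a safety defect. It is cautious, and what it would cost is Japanese data at doses already given elsewhere, since "no dose will be included which has not been previously studied in the FIH study".
- That QTcF is known to be free of heart rate. The SAP checks this only afterwards. The point is that the stop does not cover the measure the SAP analyses.

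Exclusion criterion 17 is affected in the same way: QTcB 450 ms equals QTcF 463.9 ms at 50 bpm and 420.6 ms at 90 bpm. But its 450 ms is an example and needs repeated values, so this adds little.

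**What to change.** In Protocol 3.3.4.2 item 5, state the trigger as a QTcF or QTcB increase of more than 60 ms from baseline, or absolute QT, QTcF or QTcB above 500 ms. Keep the two-subject and repeat-ECG conditions.

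In 5.2.5.1 b), state that QT, QTcF and QTcB are used, with QTcF machine-read or calculated from the recorded QT and RR (also after a manual correction), and that a central override is judged on the same values. Naming QTcF in exclusion criterion 17 is optional.

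Every condition that stops escalation now would still do so, and the late-stop gap closes. The working part is the QTcF change limit. QTcF always lies between QT and QTcB, so naming it in the 500 ms limb is for completeness only.

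The cost is wording at two places, with no extra ECGs and no new SAP output. If the machine does not report QTcF, the site must calculate it at each time point with a checked formula, which brings some risk of error. Early stops on QTcB when heart rate rises remain possible.
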